**Table 9 Analysis Visit Windows (Clinic Visits Only)**

Protocol Specified Visit Number	eCRF Visit Label	Analysis Visit	Target Study Day	Start (days)	Stop (days)
Visit 1a	SCR	Screening	-15	-45	-7
Visit 1b	SCR	Screening	-15	-45	-7
Visit 2	WK0	Day 1	1	-6	14
Visit 3	WK4	Week 4	29	15	36
Visit 4	WK6	Week 6	43	37	57
Visit 5	WK10	Week 10	71	58	85
Visit 6	WK14	Week 14	99	86	113
Visit 7	WK18	Week 18	127	114	148
Visit 8	WK24	Week 24	169	149	190
Visit 9	WK30	Week 30	211	191	239
Visit 10	WK38	Week 38	267	240	295
Visit 11	WK46	Week 46	323	296	365
Visit 12	WK58	Week 58	407	366	449
Visit 13	WK70	Week 70	491	450	512
Visit 14	WK76	Week 76	533	513	575
Visit 15	WK80	Follow-up	Last dose	Last dose +1	Last dose +30
Visit 1 OLE	WK76	Week 76	533	513	575

Protocol Specified Visit Number	eCRF Visit Label	Analysis Visit	Target Study Day	Start (days)	Stop (days)
Visit 2 OLE	WK88	Week 88	617	576	659
Visit 3 OLE	WK100	Week 100	701	660	785
Visit 4 OLE	WK124	Week 124	869	786	953
Visit 5 OLE	WK148	Week 148	1037	954	1121
Visit 6 OLE	WK172	Week 172	1205	1122	1289
Visit 7 OLE	WK196	Week 196	1373	1290	1457
Visit 8 OLE	WK220	Week 220	1541	1458	1625
Visit 9 OLE	WK244	Week 244	1709	1626	1793
Visit 10 OLE	WK268	Week 268	1877	1794	1962
Visit 11 OLE	WK292	Week 292	2046	1963	2130
Visit 12 OLE	WK316	Week 316	2213	2131	
Visit 12 OLE		Follow-up	Last dose	Last dose +1	Last dose +30

## 10 STATISTICAL AND ANALYSIS ISSUES

### 10.1 Adjustments for Covariates

The categorical, randomization stratification variable (i.e., Week 4 A4 value [0 =  $A4 \leq 4 \times ULN$ ; 1 =  $A4 > 4 \times ULN$ ]) will be used in all efficacy analyses. The categorical variables treatment group (0 = placebo, 50 = 50 mg QD tildacerfont, 100 = 100 mg QD tildacerfont, and 200 = 200 mg QD tildacerfont) and sex (0=male, 1=female) will also be included efficacy analyses.

The log baseline serum A4, as a continuous covariate, will be included in a model for the analysis of change from baseline in A4 without the randomization stratification variable. The baseline GC dose, as a continuous covariate, will be included in models for the analysis of serum A4 and the change from baseline in GCs. The baseline value of continuous efficacy endpoints will be included in statistical models, such analysis of covariance (ANCOVA) or mixed-model for repeated measures (MMRM) as a continuous covariate for exploratory endpoints.

When fitting a logistic regression model, the treatment will be coded as 0 = placebo, 50 = 50 mg QD tildacerfont, 100 = 100 mg QD tildacerfont, and 200 = 200 mg QD tildacerfont. The treatment will be an explanatory variable in the model.

## **10.2 Handling Dropouts or Missing Data**

Every effort will be made by the Sponsor to ensure completeness of data collection. Missing data will be imputed as described in the following sections.

In the subject listing, all collected and all imputed values, if any, will be presented.

### **10.2.1 Handling of Efficacy Data**

For missing A4 data, a retrieved dropout approach will be used which missing endpoint data for subjects who discontinued early will be imputed using data collected from subjects after discontinuation of study drug. If insufficient data exists ( $n \leq 5$  per treatment group) to perform a retrieved drop out approach assuming missing at random (MAR), a multiple imputation approach will be used assuming missing not at random (MNAR) ([Section 13.4](#)).

### **10.2.2 Handling of Questionnaire Data**

A total score for questionnaires will be calculated so long as  $> 50\%$  of the items are non-missing. Otherwise, the total score will be set to missing.

### **10.2.3 Handling of Laboratory Data**

A retest value will be used if the first test is invalidated, e.g., specimen hemolyzed. For non-PK laboratory values that are continuous in nature but are presented as either above or below the respective quantitation limits, the following imputations will be made for the purposes of summarization:

- If value is listed as  $< X$ , then the imputed value will be  $X/2$
- If a value is listed as  $\leq X$ , then the imputed value will be  $X$
- If value is listed as  $> X$ , then the imputed value will be  $X+1$
- If a value is listed as  $\geq X$ , then the imputed value will be  $X$

## 10.2.5 Handling of Safety Data

### 10.2.5.1 Adverse Events

If the time of onset (before or after intake of study drug) cannot be determined whether an AE is treatment-emergent because of a partial onset date, the event will be counted as a TEAE.

Adverse events with incomplete onset and end dates will have their dates imputed and then will be evaluated for their treatment-emergent status.

Incomplete adverse event onset date/time:

- If day is missing:
  - If month and year are the same as the month and year of first study drug exposure, then impute to the date of first study drug exposure.
  - Else if day is missing and year or month is not the same as the year and month of first study drug exposure, then impute as Day 1 of the month.
- If month is missing:
  - If year is the same as the year of first study drug exposure, then impute to the date of first study drug exposure.
  - Else if year is not the same as the year of first study drug exposure, then impute as January 1.
- If year is missing then impute to the date of first study drug exposure.
- If imputed start date is after AE end date, then impute the start date to the AE end date.

Incomplete adverse event end date/time:

If only have a YEAR, impute as December 31.

Else if only have YEAR and MONTH, then impute to last day of the month.

Otherwise missing, no imputation. If severity or relationship of an AE to study drug is not recorded, the severity or relationship will be imputed as “severe” or relationship as “possibly related,” for analysis purposes. All efforts will be made to ensure no missing severity or relationship of an AE to study drug prior to database lock finalization.

### 10.2.5.2 Concomitant Medications

If the start date of a medication is missing, the medication will be considered to have started prior to the study. Such a medication may also be considered concomitant, depending on the stop date or lack thereof. If the stop date of a concomitant medication is missing, then the medication

will be treated as ongoing. If the start date of a medication is missing, the stop date will be used to determine whether or not it is concomitant. Medications with other incomplete start dates or end dates will be imputed as follows:

Incomplete medication start date/time:

- If only have a YEAR, impute as January 1.
- Else if only have YEAR and MONTH, impute as Day 1 of month.
- Otherwise missing, no imputation.

Incomplete medication end date/time:

- If only have a YEAR, impute as December 31.
- Else if only have YEAR and MONTH, then impute to last day of the month.
- Otherwise missing, no imputation.

### **10.3 Primary Analyses and Safety Data Monitoring**

The primary efficacy analysis will be conducted as when all subjects complete the Week 18 visit of the Treatment Period in Part A and the data has been hard-locked for analysis. The final analysis will occur after the last subject has completed the Week 76 visit or if the Sponsor discontinues the study.

An external, independent data safety monitoring board (DSMB) will review the available safety data (both blinded and unblinded) from this study periodically. The DSMB will advise the Sponsor of any trends or safety issues that may impact the study or study subjects and provide recommendations to the Sponsor if needed per the DSMB Charter.

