Another important goal of treatment in CAH is the reduction of GC dose requirements ([Speiser 2018](#)). To that end, Part C of this study and the optional Open-Label Extension Period will explore the potential GC-sparing effects of tildacerfont in subjects with elevated baseline A4 who are able to achieve A4 control on tildacerfont. In Part C, and in the optional Open-Label Extension Period, eligible subjects may begin to reduce their GC doses. The change from baseline in GC dose and the proportion of subjects with at least a 5 mg/day HCe reduction from baseline in GC dose at the end of Part C (while maintaining A4 \leq ULN) will be evaluated as an exploratory efficacy endpoint.

The placebo Run-in Period provides subjects time to acclimate to participation in a clinical study, which can often change subject behavior, before active therapy with tildacerfont is initiated. In the case of CAH patients participating in this study, behavior changes may include improved dosing adherence to background GC medications and alterations in daily routine (such as changes to sleep schedules and mealtimes) to accommodate morning laboratory assessments and daily study drug dosing with an evening meal. Such changes may produce effects on biomarkers independent of tildacerfont. The Run-in Period thus serves to ensure that subjects are on a stable baseline regimen of GC replacement therapy before the start of tildacerfont dosing and provides for more accurate and stable baseline data.

The 70-week treatment duration and the optional Open-Label Extension Period will provide longer-duration information than previous Phase 2 clinical studies on the effects of tildacerfont on adrenal hormones and on whether effects on other clinical outcome measures of concern can be achieved with tildacerfont. The 30-day post-treatment washout period allows for adequate safety follow-up and analysis of any HPA axis rebound after the last dose of study drug.

The schedule of study visits interspersed with telephone contacts provides an appropriate balance between minimizing subject burden and closely monitoring subjects for safety and response to therapy.

Study drug will be taken with a meal because Phase 1 clinical studies showed that taking tildacerfont in a fed state improves drug absorption. The meal should contain approximately 25 -50% fat content because high fat intake with study drug may increase drug accumulation.

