6.5.1.6 Post-Treatment Glucocorticoid Dosing

Upon completion of the Treatment Period, subjects will maintain the GC regimen and mineralocorticoid regimen (as applicable) established during Part C until the 30-day follow-up visit unless the Investigator determines that the subject's clinical status necessitates a dosing change. After completion of the study, GC therapy will be managed at the discretion of the subject's treating physician.

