9.5 Primary and Final Analyses

The primary analysis is planned after all subjects have completed Week 18. The Sponsor and CRO will be unblinded to treatment assignment in Part A at the time of the primary analysis, but Investigators, who conduct the study, and subjects will remain blinded.

The final analysis will occur after the last subject has completed the last follow-up visit or if the study is discontinued by the Sponsor.

A clinical study report will be completed for the study with results up to Week 76/80. An addendum to the clinical study report will be completed to summarize the results from Week 76 up to Week 316/320.

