### **9.3.25 Adverse Events**

AEs are those AEs with onset date from the signing of the ICF until the end of the follow up period.

Treatment-emergent adverse events (TEAEs) are defined as any AEs, regardless of relationship to study drug, that have an onset or worsening in severity on or after the first dose of double-blinded study drug (within Treatment Period) until 30 days after the final dose of study drug (safety follow-up visit).

If a subject discontinues study drug but remains in the study, AEs with onset date after 30 days of last dose of study drug until the end of the follow up period will be considered post-treatment adverse events.

Related TEAEs are those reported by investigators as possibly related, probably related, or definitely related to the study drug.

AESIs are events that must be monitored on an ongoing basis as defined in Protocol Section 8.3.8 and identified in the AE eCRF page. The AESIs that are serious AEs (SAEs) will be handled according to guidelines from the National Cancer Institute Common Terminology Criteria for Adverse Events (CTCAE 2017) version 5.0, as described in Protocol Section 8.3.3.1.

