### **13.2 Final Efficacy Analysis**

The Final Efficacy Analysis will occur after the last subject has completed the study Week 76 visit or if the study is discontinued by the Sponsor. The data from study Week 18 through Week 76 will be frozen prior to the final analysis.

The scheduled visits included in this treatment period include study Week 24, Week 30, Week 38, Week 46, Week 58, Week 70, Week 76 visits. Exploratory Efficacy Analyses 3.7 to 3.11 and Safety Endpoints 5.1, as shown in [Table 1](#), will be analyzed at the final analysis.

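### The SAP lets the final safety analysis be locked at the last subject's Week 76 visit, before the 30-day off-drug follow-up that Protocol 9.5 and the SAP's own definitions require

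*SAP*

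**What the plan says.** **Trigger and freeze in the SAP.** SAP 10.3: "The final analysis will occur after the last subject has completed the Week 76 visit or if the Sponsor discontinues the study". SAP 13.2 repeats the trigger, lists visits from Week 24 to Week 76 and adds: "The data from study Week 18 through Week 76 will be frozen prior to the final analysis". It assigns to this analysis "Exploratory Efficacy Analyses 3.7 to 3.11 and Safety Endpoints 5.1"; in SAP Table 1, item 5.1 is AEs and SAEs.

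**Trigger and report in the protocol.** Protocol 9.5: "The final analysis will occur after the last subject has completed the last follow-up visit or if the study is discontinued by the Sponsor". On the report it says: "A clinical study report will be completed for the study with results up to Week 76/80".

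**Other SAP sections that keep the follow-up in scope.**
- Section 9.3.25 counts treatment-emergent events "until 30 days after the final dose of study drug (safety follow-up visit".
- Section 5.2.6.1 collects AEs to about 30 days after the last study drug.
- Section 5.2.6.5 lists clinical labs at Week 80.
- Table 9 defines a Follow-up window from last dose +1 to last dose +30 days.
- Section 9.3.5 treats a subject as having completed the main study only once the final follow-up visit is done.

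**Precedence.** SAP Section 4 says departures from the protocol's planned analyses are described in Section 15, and that the SAP prevails where the two are inconsistent. Section 15 lists changes to the definitions of treatment completion and study completion. It does not mention the timing or data scope of the final analysis.

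**The concern.** The month at issue has a stated purpose. Protocol 4.2: "The 30-day post-treatment washout period allows for adequate safety follow-up and analysis of any HPA axis rebound after the last dose of study drug". During it, under Protocol 6.5.1.6, "subjects will maintain the GC regimen and mineralocorticoid regimen (as applicable) established during Part C until the 30-day follow-up visit", unless the Investigator judges that clinical status requires a change. That regimen may have been lowered in Part C. For a subject who completes Week 76 and stops, this is the only observed time with tildacerfont withdrawn, possibly on a lower glucocorticoid dose than at entry. Adrenal insufficiency after withdrawal and late liver findings would appear here.

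After Part C only subjects who decline the extension have this period (Protocol 4.1.1), and the extension has its own SAP (SAP Section 4). The final analysis under the present SAP is therefore where their follow-up should be reported. If it is locked at the SAP's trigger, the treatment-emergent tables may not cover the window that Section 9.3.25 defines for them.

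**Working it through.** **1. Reproduce the plan's calendar.** SAP Section 5 gives up to 87 weeks for the main study: 45/7 + 6 + 70 + 30/7 = 86.7 weeks, which rounds up to 87. The 30-day follow-up is inside that total.

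**2. Date the two triggers for the last subject.** Take the last dose at the Week 76 visit.
- SAP trigger: 76 × 7 + 1 = Day 533, as in the schedule and Table 9.
- Protocol trigger: 533 + 30 = Day 563, or (563 − 1)/7 = 80.3 weeks, which matches the Week 80 label.
- Gap: 30 days (30/7 = 4.3 weeks).

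**3. Share of the safety window.** Treatment lasts 70 × 7 = 490 days. The treatment-emergent window for a Week 76 completer who does not extend is 490 + 30 = 520 days. The part at risk is 30/520 = 5.8% of the window, and all of its off-drug part.

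**4. Who is affected, under each reading of the text.**

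| Reading | Follow-up lost |
|---|---|
| Lock on the trigger date, using all data in hand | A non-extending subject whose last dose was d days before the lock loses 30 − d days if d < 30, and none otherwise |
| Freeze applied by visit label, Week 76 last | The whole follow-up of every subject who does not extend |
| Freeze applied by Table 9 study-day windows | Unclear: the Week 76 window is Days 513–575, which contains follow-up Days 534–563 |

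The third row matters because, for a subject who stops at Week 76, an assessment in the off-drug month fits both the Week 76 window and the Follow-up window. Two programmers could reach different cutoffs and each cite the SAP.

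**5. Does Section 14 repair it?** Sections 14.1, 14.1.1 and 14.1.2 tabulate AEs by Parts A, B and C. They name no follow-up period and give no cutoff of their own.

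**6. Count.** Planned randomisation is 72 with 15% dropout, so about 72 × 0.85 = 61 completers. The share who decline the extension is not stated, nor is the pattern of finishing dates, so no count follows.

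**The case against.** The other side has good points, and several stand.

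- **The SAP never says follow-up is excluded.** It does not say the freeze is limited to Week 76 only, and the freeze sentence sits in an efficacy section. Read as an exclusive limit, it would also discard Part A safety data, which nobody intends. It more naturally describes what is added after the Week 18 lock. This stands against any claim that the month is definitely cut. It does not remove the problem, because the same section puts the AE and SAE endpoint in this analysis and lists no visit after Week 76.
- **The trigger sets an earliest date.** The analysis comes after the last Week 76 visit and could wait for follow-up. True, but nothing in the SAP requires it to wait.
- **Protocol 9.5 is itself loose.** Protocol 4.4.1 and 4.4.2 define the end of the study by the last subject's last follow-up visit, which could be read as extension follow-up near Week 320. The SAP's Week 76 trigger may have been meant to separate the main study from the extension. That is a plausible motive, and a reason not simply to copy the protocol's sentence, but the change is still undeclared.
- **Ongoing oversight is untouched.** SAE reporting and DSMB review continue whatever the lock date. That protects subjects; it does not complete the tables.

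A reader might also infer that the Week 80 data belong to no analysis at all. The documents do not support that: Protocol 9.5 gives the main report a scope to Week 76/80, and this SAP exists to support that report.

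**Conclusion.** The conflict holds as an undeclared inconsistency between a stated SAP rule and both the protocol and the SAP's own safety definitions. Followed as written, the final safety tables may omit or truncate up to 30 days of off-drug follow-up (to about Day 563) in subjects who do not enter the extension. At the least this touches those whose last dose falls within 30 days of the lock; if the freeze is applied by visit label it touches all of them. The Day 533 and Day 563 figures assume the last dose is taken at an on-schedule Week 76 visit.

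Three stronger conclusions should not be drawn:
- **A number of subjects.** One could assume that 25–75% of about 61 completers decline the extension and arrive at 15–46. That rate is not in the documents, and the range applies only under the visit-label reading.
- **That safety will look better than it is.** This presumes an exclusion the SAP does not state.
- **That the freeze removes a planned rebound analysis of A4 or ACTH.** SAP Table 1 and Section 13 specify no hormone analysis after Week 76, so none is there to lose.

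**What to change.** Amend SAP 10.3 and 13.2 so that the final analysis occurs after every subject has completed the 30-day follow-up visit, entered the extension or left the study. Freeze main-study data through Week 76/80, meaning last dose +30 days for subjects who do not enter the extension. Worded this way, the trigger does not wait for extension follow-up. The clause on sponsor discontinuation can stay.

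Add the Week 80 follow-up visit to the list in SAP 13.2 so that follow-up AEs and labs enter the Section 14 summaries, and say there how events in the off-drug month are tabulated. If the Week 76 trigger is deliberate, declare and justify it in Section 15 and state where the follow-up data will be reported.

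The cost is a few sentences of SAP text and about 30 days' delay to the final lock. No protocol procedure or data collection changes.

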### **10.4 Multicenter Considerations**

This trial will be conducted at approximately 110 study centers in the United States, Europe, and other regions. Data from all study centers will be pooled for efficacy and safety analyses. Because the number of subjects at each center is likely to be small, no analyses will be performed by center.

## **10.5 Multiple Comparisons, Multiplicity**

To control family-wise error rate, statistical hypothesis testing for the primary endpoint will be hierarchically dose ordered, testing first the 200mg dose versus placebo at 0.05 2-sided; then followed by the 100mg dose versus placebo at 0.05 2-sided if the 200mg dose reaches  $p \leq 0.05$ ; and finally, the 50mg dose versus placebo at 0.05 2-sided if the 100mg dose reaches  $p \leq 0.05$ .

Secondary and exploratory endpoints will not be subject to alpha control, rather these endpoints will be interpreted nominally at the 2-sided 5% level.

## **10.6 Active-Control Studies**

The placebo group will serve as a comparator in the primary analysis of this study.

## **10.7 Examination of Subgroups**

Subjects will be categorized into the following common subgroups for the purposes of evaluating the primary and secondary efficacy endpoints.

- Baseline A4 ( $\leq 4 \times \text{ULN}$ ,  $> 4 \times \text{ULN}$ )
- Baseline GC dose in HCe ( $\leq 30 \text{ mg/day}$ ,  $> 30 \text{ mg/day}$ )
- Sex (Male, Female)
- Age
  - o  $\leq 30 \text{ years}$ ,  $> 30 \text{ years}$
  - o  $\leq \text{median age of the ITT Analysis Set}$ ,  $> \text{median age of the ITT Analysis Set}$
- Geographic Region ((i) North America, Not North America and (ii) NA, Latam, Europe, APAC)

Forest plots will be generated to display the primary efficacy, secondary efficacy, and select safety evaluations from the above subgroups, along with the overall results.

Additional subgroups specific to only select endpoints are specified in the appropriate section in the SAP.

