### 9.3.28 Geographic Regions

About 75 study centers will participate in this study. Three geographic regions will be classified by the countries where these study centers are located: North America, European Union and United Kingdom, and the rest of the world.

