### 13.3.3 Dose Response Modeling and Testing

Statistical testing for dose response will be performed using the repeated measures random coefficients mixed-effects model described in [Section 13.3.2](#). A4 values will be log transformed prior to analysis. The model will comprise of the log A4 change from baseline through to study Week 18, i.e. though 12 weeks of double blind randomized treatment; note the actual time, in days, from baseline to each post baseline A4 value through to study week 18 will be used in this analysis. Randomized treatment group and sex will be included in the model as class factors and baseline GC dose (in HCe) as continuous covariate. Subject specific intercept, time (in days)

and time x time random effects will be included. Further, randomized treatment by time and randomized treatment by time x time interactions will be included. The model will be fitted using maximum likelihood estimation. If the variance component for time or time x time are estimated to be zero then the corresponding term (or terms) will be retained in the model as fixed effects and the analysis re-run.

To test the union intersection hypothesis  $H_{0L} \cap H_{QL}$ , the model will be fitted with and without the randomized treatment by time and randomized treatment by time squared interactions terms. The difference in -2 log likelihood between models will be compared to the  $\chi^2_{df}$  cumulative distribution function on the appropriate degrees of freedom (i.e.  $df = 6$ ), this will provide the p-value to determine if the union intersection hypothesis can be rejected at the 10% alpha level; if so then there is evidence for a treatment effect of tildercerfont over placebo.

The fitted A4 change from baseline versus time profile will be extracted from the model for each randomized treatment and displayed graphically, superimposed upon the A4 time profiles for individual subjects.

Note, the programming of the repeated measures random coefficients mixed-effects model is particularly complex, hence example SAS codes perform the analysis are presented in Appendix D.

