### 13.3.5.3 Subgroup Analyses

The primary analysis of A4 as described in [Section 13.3.3](#) repeated for each subgroup specified in [Section 10.7](#) for the ITT Analysis Set. A forest plot of the estimated treatment effects at Week 18 by dose level and subgroups will be provided.

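### Subgroup results come from separate refits of the primary model with no treatment-by-subgroup interaction, so the plan yields nothing on whether the effect differs between levels

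*SAP*

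**What the plan says.** SAP 10.7 introduces its list with "Subjects will be categorized into the following common subgroups for the purposes of evaluating the primary and secondary efficacy endpoints". The factors are baseline A4, baseline GC dose, sex, age cut at 30, age cut at the median, and "Geographic Region ((i) North America, Not North America and (ii) NA, Latam, Europe, APAC". The results go into forest plots beside the overall result. Protocol 9.4.8 lists the same factors except region.

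The operative text is SAP 13.3.5.3. The analysis of SAP 13.3.3 is "repeated for each subgroup specified in" SAP 10.7, in the ITT set, and "A forest plot of the estimated treatment effects at Week 18 by dose level and subgroups will be provided". The only interactions in that model are with time: "randomized treatment by time and randomized treatment by time x time interactions will be included". Its test is a likelihood ratio test on 6 degrees of freedom: "this will provide the p-value to determine if the union intersection hypothesis can be rejected at the 10% alpha level". The only provision for a difficult fit begins "If the variance component for time or time x time are estimated to be zero then the corresponding term (or terms" and keeps such terms as fixed effects.

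Neither document gives a treatment-by-subgroup term, a minimum subgroup size, or a rule for reading subgroup results. On region, SAP 9.3.28 says "Three geographic regions will be classified by the countries where these study centers are located": North America; the European Union and United Kingdom; and the rest of the world.

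**The concern.** A separate fit in each level answers whether a dose can be distinguished from placebo in that level. It does not answer whether the effect differs between levels, which is the reason for looking at subgroups. With a uniform effect, two small samples will sometimes fall on opposite sides of a significance threshold by chance, and nothing in the planned output would correct that impression. Separate fits also discard what the other level says about residual variance and covariate effects.

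Three further points need no calculation:

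- Sex is a model term but is constant inside each sex subgroup, and the SAP does not say that it drops.
- SAP 10.7 uses two and four regions where SAP 9.3.28 defines three.
- Randomisation is stratified by Week 4 A4 (SAP 5.1), whereas baseline A4 averages Day 1, Week 4 and Week 6 (SAP 9.3.10), so the A4 subgroup is not the randomised stratum.

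**Working it through.** **Levels and model size.** Six two-level splits plus one four-level split give 6 × 2 + 4 = 16 listed levels. North America appears in both region splits, so 15 are distinct. Fixed effects: 1 intercept + 2 time + 3 treatment + 3 treatment-by-time + 3 treatment-by-time-squared + 3 covariates (log baseline A4, sex, baseline GC dose) = 15. Variance parameters: 3 random effects + 1 residual = 4. With 72 subjects in four arms, an equal split leaves 72/4/2 = 9 per arm, and four regions average 72/4/4 = 4.5 per arm.

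**The plan's own figures (protocol 9.2, SAP 7).** 15/(1 − 0.15) = 17.6, rounded up to 18 per group; 4 × 18 = 72, as stated. For 15 per group, difference 50 and SD 30, the standard error is 30 × √(2/15) = 10.95, and power is Φ(50/10.95 − 1.96) = Φ(2.60) = 99.5%. The stated 80% therefore holds as a lower bound. Power of exactly 80% at n = 15 needs a difference of (1.96 + 0.84) × 10.95 = 30.7 points.

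**Disagreement between halves under a uniform effect.** This compares one dose with placebo at two-sided 5%. If each half has power p, the chance that exactly one half is significant is 2p(1 − p). Power is from the noncentral t. The last two columns are simulated (1,500 trials per row, six mutually independent random half-splits).

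| True difference | Per arm | p in each half | 2p(1 − p) | Any of six splits, 200 mg | Any split, any dose |
|---|---|---|---|---|---|
| 50 | 18 | 91.3% | 16% | 44% | 74% |
| 50 | 15 | 84.7% | 26% | 63% | 88% |
| 30.7 | 18 | 53.2% | 50% | 88% | 99% |
| 30.7 | 15 | 45.0% | 50% | 85% | 98% |

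The simulation lets arm sizes vary within halves. Its per-split figures for 200 mg at 50 points are a little higher than the formula's, at 18.5% and 30.5%.

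**Regions.** No enrolment by region is given, so these are assumed sizes. With 72 subjects and 18 per arm, the chance that a region has at least one empty arm is 0.9% for 18 subjects, 9% for 12, 33% for 8 and 59% for 6. The chance that at least one of four regions has an empty arm is about 4% for 18/18/18/18, 63% for 36/12/18/6 and 99% for 44/4/20/4. In a rough simulation of the random-coefficients model (about 90 runs per scenario, assumed variances), an 18-subject region could be fitted in about 99% of runs. The nominal 10% test rejected in about 34% of runs with no effect. That figure depends on the assumed variances and only suggests that the test is unreliable at this size.

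**What an interaction test offers.** Under a uniform effect it is falsely significant in 5% of trials per factor, or 1 − 0.95⁶ = 26% for any of six if independent. For halves of n/2 per arm, the standard error of the difference in effects is 30 × √(4/(n/2)): 20.0 at n = 18 and 21.9 at n = 15. Power for a 25-point difference between halves is Φ(25/20.0 − 1.96) = 24% and Φ(25/21.9 − 1.96) = 21%. For 50 points in one half and none in the other it is 71% and 63%.

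**The case against.** The strongest reply is that SAP 13.3.5.3 asks for a forest plot of estimates, places it among the sensitivity analyses of the primary result, and sets no significance rule for subgroups. Read as intervals beside the overall effect, the plot misleads far less. This stands in part. But the analysis to be repeated is itself a test that the SAP reads as evidence of a treatment effect. SAP 10.7 also extends the subgroups to the secondary endpoints, the first of which carries a p-value per dose (SAP 13.4.1) read nominally at 5% (SAP 10.5). P-values by level are a natural product of the plan, and a comparison between levels is not.

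A second reply is that the interaction test is weak and the pooled model is larger. With full time terms a two-level factor adds up to 1 + 2 + 3 + 6 = 12 fixed effects. That is true, and it is why the result must be labelled descriptive. Two separate fits nevertheless use 2 × 19 = 38 parameters, against 15 + 12 + 4 = 31 in the pooled model.

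Some stronger readings are not supported:

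- A reader might infer that a uniform effect will usually look like benefit in one level only. For an equal split 2p(1 − p) cannot exceed 50%, and at the planning values it is 16 to 26%. An 80/20 split would reach 55 to 65%, but the documents give no subgroup shares.
- A reader might infer that the four-region fits will often be inestimable. That rests entirely on assumed enrolment, and an empty arm removes that arm's contrast rather than the whole fit.
- The baseline A4 subgroup is not biased. It is measured before double-blind dosing, and sex, age, GC dose and region are not stratified either.
- The refits are not the plan's means of deciding whether subjects with higher hormones need a higher dose. Protocol 4.2 and SAP 6 assign that to dose escalation after Part A.

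**Conclusion.** The concern holds as a weakness of method that is cheap to repair. The plan refits a 19-parameter model level by level and produces nothing on whether effects differ. If levels are read by their own p-values, a uniform effect at the planning values would give at least one disagreement for 200 mg among six splits in about 44 to 63% of trials, and in 85 to 88% near an effect giving 80% power at 15 per arm.

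These figures assume normal outcomes, equal splits and one Week 18 comparison per dose. They use the protocol's percent-change inputs because no log-scale SD is given. The two age splits overlap in practice, whereas the simulated splits were independent. The regional figures are conditional on enrolment that is not stated. The conflict between SAP 9.3.28 and 10.7 and the constant sex term follow from the text alone. The constant sex term is minor: it simply drops out.

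**What to change.** In SAP 10.7 and 13.3.5.3, replace the separate refits with one ITT model per two-level factor: the primary model plus subgroup and treatment-by-subgroup terms, with the time terms needed for Week 18. For sex, the main effect is already in the model. In the forest plot, report Week 18 dose-versus-placebo estimates with 95% CIs by level and a nominal interaction p-value. Label the display descriptive, and state that a non-significant interaction does not show that effects are equal.

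Use one region definition throughout the SAP. Model only North America versus not North America, and summarise finer regions descriptively. For the A4 factor, use the Week 4 randomisation stratum, or show it beside baseline A4 so that the protocol's own subgroup is kept.

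The cost is SAP wording and modest code changes. The statistical price is the assumption of common covariate effects and variances across levels.
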